UPWARD and each UPWARD Supplemental Arm will have a unique study fact sheet. The online study fact sheet will accurately describe the general goals of the study and the nature of the participant's role in the study. Participants will be given the ongoing opportunity to ask any questions regarding confidentiality, participation schedule, or any other aspect of the study in the first call with the MGH team and in all subsequent contacts with study team members. After reading the study fact sheet, study staff will obtain verbal consent for participation. In addition, participants will review key points of the study with study staff, will be provided with contact information and encouragement to contact study staff members with questions via email or phone, and will be encouraged to print and retain personal copies of the study fact sheet. Consented subjects will be sent a copy of the phone consent document. This consent form will include a summary of privacy policies and date of consent. Individuals who do not provide verbal consent will be informed that it is not possible for them to participate in the study and we will provide them with a list of links to depression information websites.

[figure not shown]
To maintain concealment, assignment will occur following the baseline assessment by telephone interview with the MGH team. Assignments will be generated using a random number table with equal probability of assignment to each group in blocks of four, which will guarantee balance for every four subjects. Randomization to study arm will be stratified based on number of prior episodes, antidepressant medication status (on medication or having discontinued at time of randomization), and baseline depressive severity based on PHQ-9 score. Women will be randomly assigned to receive MMB ($n = 300$) or UC ($n = 300$).

Study staff will also obtain contact information for community providers and consent from study participants to be in touch with these providers. This contact information will be used to send a letter describing the study and providing the consult line and availability of study doctors for questions. Additionally, we will reference the MGH Center for Women's Mental Health's website, www.womensmentalhealth.org, as a perinatal resource center that provides evidence-based safe practices for both the study participant and their clinician during pregnancy.

UPWARD Supplemental Arms

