The final 100 participants in the UPWARD sample of 600 individuals will participate in an abbreviated version of the UPWARD procedures. These 100 women will be recruited via the same platform of BabyCenter, screened and enrolled based on the same entry criteria, and similarly randomized to the MMB intervention or Usual Care. However, the only differences will be that these final participants in this group of 100 who are randomized to the treatment group will not receive the coaching that is typically involved in the MMB intervention. This will further investigate our research aims to assess the extent to which this modified version of MMB is still an effective means of preventing depressive relapse in a perinatal population. Moreover, these final 100 participants will not receive any follow-up clinical interviews or relapse determination calls after the initial screening and baseline calls. Participants will be randomized after the baseline call, either through a phone conversation or via email. They will instead be prospectively followed through 3 months postpartum via the same battery and schedule of self-report questionnaires given to the other UPWARD participants through this timepoint. If any participant endorses items 3, 4, or 5 on the C-SSRS via these self-report questionnaires, the same suicidality safety protocol will be triggered as outlined below. The information about the delivery and newborn outcomes that would typically be collected during the 3 months postpartum interview will now be administered as a self-report survey with the rest of the questionnaires for this timepoint.

Table 2. UPWARD Extension Measurement Schedule

UPWARD Study	Baseline	M1	W6	M2	Post-Intervention	M3	M4	M5	3T	M6	M7	M8	3PP
MINI full	x												
MINI mood	x				x				x				x
MADRS	x				x				x				x
EPDS	x	x	x	x		x	x	x	x	x	x	x	x
PHQ-9*	x	x	x	x		x	x	x	x	x	x	x	x
CS-S**	x												
CGI	x				x				x				x
PGI	x	x	x	x		x	x	x	x	x	x	x	x
GAD-7	x	x	x	x		x	x	x	x	x	x	x	x
PSS-10	x					x			x				x
WHODAS 2.0	x					x			x				x
CSQ-8 (UC)	x					x							
CSQ-8 (MMB)						x							
CTQ	x												
PROMIS	x												
FFMQ	x		x			x							
RRS	x		x			x							
SCS	x		x			x							
SSQ-SF	x					x							x
RSQ-MEP	x												
LEL	x												
LEIDS-R	x		x			x							
EQ	x		x			x							
CSI	x												
AToM	x					x			x				x
PSA	x		x			x			x				
PSQI	x					x							x
Positive Mood Diary	x		x			x							

DPES Joy Subscale	x		x		x					x
CERTS Unresolution Subscale	x									

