Perceived Stress Scale (PSS): The PSS is a 10-item self-report questionnaire that assesses the severity of recent psychosocial stressors.

Life Events List (LEL): The LEL is a 24-item scale used to assess multiple life stressors.

Functional Status

WHO Disability Assessment Schedule 2.0 (WHODAS 2.0): The WHODAS 2.0 will assess functional status.

Intervention Exposure and Satisfaction

Client Satisfaction Questionnaire (CSQ-8): The CSQ-8 is an 8-item questionnaire that will be used to assess satisfaction with digital MMB and UC.

Usual Care Characterization

To characterize the nature of UC for all participants, accurate tracking of care received, including pharmacotherapy, psychotherapy, and other interventions, will be conducted using the Treatment Tracking Sheet used in previous NIMH funded studies of perinatal depression at the MGH site. This sheet will be completed by study staff for each subject throughout their participation.

Personalization Variables

Sarason Social Support Questionnaire – Short Form (SSQ-SF): The SSQ-SF is a 12-item scale designed to assess social support.

Leiden Index of Depression Sensitivity – Revised (LEIDS-R): The LEIDS-R is a 34-item scale that measures cognitive reactivity to sad mood.

Couple Satisfaction Inventory (CSI): The CSI is a 16-item measure of partner relationship qualities.

Childhood Trauma Questionnaire (CTQ): The CTQ is a 28-item measure of childhood abuse/adversity.

Attitudes Toward Motherhood Scale (AToM): The AToM is a 12-item scale that measures women's beliefs about motherhood.

Pittsburgh Sleep Quality Index (PSQI): The PSQI is a 9-item scale that measures sleep quality.

Patient-Reported Outcomes Measurement Information System (PROMIS) Social Isolation Subset: The PROMIS social isolation 8-item short form subset is a set of 8 questions to assess perceptions of being avoided, excluded, detached, disconnected from, or unknown by, others.

Dispositional Positive Emotion Scale (DPES): The DPES Joy Subscale is a 6-item questionnaire that measures one's dispositional tendency to feel joy in life.

Cognitive Emotion Regulation Questionnaire (CERQ): The CERQ Acceptance Subscale is a 4-item questionnaire that measures the cognitive component of emotion regulation characterized by acceptance of one's situation.

Cambridge Exeter Repetitive Thoughts Scale (CERTS): The CERTS Unresolution Subscale is a 4-item questionnaire that measures unresolved ruminative thinking styles.

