5	Facing Difficulties	Increasing use of mindful attention at the first step in responding effectively to difficulties, including difficult internal experience such as sadness; decreasing judgmental thoughts and avoidant responses to difficulties.
6	Thoughts Are Not Facts	Decreasing affective reactivity to thoughts previously associated with depression; learning to “de-center” from difficult thoughts, recognizing one’s personal patterns of recurring thoughts,
7	Building Your Plan of Action	Identifying unique ‘signatures’ of mood worsening; identifying activities that improve or deteriorate mood; developing action

		plans to implement during periods of high risk; using mindfulness practice explicitly to guide action plan steps.
8	Supporting Your Practice in the World	Emphasizing the importance of regular self-care routines, identifying 'your daily routine of mindfulness practice'; reinforcing links between mindfulness practices, wellbeing and maintenance

MMB for Moms may be a promising intervention for pregnant women with suicidal ideation, as it delivers digitally both the content and structure of in-person MBCT. The standard MMB for Moms program will be implemented for participants in UPWARD Supplemental Arm 2; however, measurement expansion for Supplemental Aim 2 will probe participant responses to the content and the potential need for additional information specific to suicidal ideation and behaviors.

Usual Care (UC). Usual care will not be constrained for any study participants, including those randomized to MMB. The study will not constrain or influence women's decisions about maintenance or discontinuation of AD for all participants. Usual care will be augmented in two ways. First, we will provide ongoing study assessments and the provision of feedback to participants based on their responses to the PHQ-9, EPDS, and clinical interviews (e.g., "Your answers seem to suggest that you are having significant symptoms of depression. We recommend that you talk with your community care provider about whether treatment or modification of treatment might help"). Usual care also will be augmented by ongoing availability of study physicians with perinatal psychiatric expertise in response to queries from community providers regarding changes or reintroduction of pharmacologic treatment during pregnancy or the postpartum period for study participants.

Prospective Follow-up and Community Outreach

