In UPWARD, UPWARD Extension and UPWARD-S, if suicidality is endorsed with a score of greater than 1 on EPDS item #10 or PHQ-9 item #9 or on any of the self-report questionnaires (such as the SITBI or CCM), subjects will be prompted to complete the CS-S to assess risk of suicidality. Study subjects will also be given the national suicide [contact]) and informed that answers to online questionnaires are not monitored in real time. A positive score on questions 3, 4, or 5 on the CS-S, indicating intention or plan for suicidality, will prompt a safety call by study physicians. Suicidality expressed during the course of clinical or qualitative interviews, either through discussion, endorsement of the suicidality item on the MINI mood module, endorsement of items 3, 4, or 5 on the suicidality module of the MINI, or via scoring >2 on the MADRS item 10, will prompt study staff to complete the CS-S with the participant. A positive score on items 3, 4, or 5 of the CS-S administered by staff will also prompt a safety call by study physicians. In addition, subjects will be told by study staff to call their community providers and go to their nearest emergency room. Endorsement of items 3-5 on the CS-S prompting a physician safety call has been the threshold used in previous studies at the collaborating site (University of Colorado Boulder). As this is a community-based study with collaboration from community physicians, these providers dictate treatment. We will notify community providers directly via phone or fax within 24 hours from report of positive scores on CS-S items 3-5.

VI. BIOSTATISTICAL ANALYSIS

Preliminary Analyses: Differences between the MMB and UC in demographic characteristics and depression related characteristics (e.g., symptom severity, comorbidity) will be assessed using Chi-square test for binary variables, Cochran Mantel Haenszel tests for categorical variables, and t-tests for continuous variables. Variables that show significant group differences and predict outcome will be entered in analyses as covariates; AD exposure will be included as a covariate. All participants will be considered evaluable for analysis (intent-to-treat sample). Significance levels will be evaluated at $p < .05$, and effect sizes reported.

Analysis for Specific Aim #1: To test the relative risk for depressive relapse and reduction of symptom burden between women randomized to digital MMB or UC.

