For the analysis of rates of relapse, we will examine time to relapse as rated by the MINI during pregnancy and across the 6-month postpartum follow up using survival analysis. Survival rates will be compared using Cox proportional hazard regression and illustrated in Kaplan-Meier curves (Collett, 1994). However, time to attrition is a competing risk that can be related to time to relapse. We will adopt the subdistribution hazard model (SHM) developed by Fine and Gray to account for the possible non-independence of the censoring mechanism.²⁵

For the continuous outcomes, we will use Hierarchical Linear Models (HLM) as our primary analytic model, which will compare change over time between groups on depressive symptom burden using the PHQ-9. HLM is flexible with respect to the nature of change over time (i.e., linear, piecewise linear, loglinear, etc.), and will accommodate the within subject correlation through the inclusion of random effects at the patient-level, accounting for the patient-to-patient deviations. Pattern-mixture models²⁶ will be used to assess whether important estimates (i.e., intervention effects) are dependent on missing data and to provide overall estimates of effects by averaging over the various missing-data patterns.

Analysis for Specific Aim #2: To explore the specific benefit of MMB relative to AD discontinuation and questions regarding personalization that are of strong interest to pregnant women and their healthcare providers.

H2a: Comparison of MMB to UC among women who discontinue AD: Our analysis will be the same as H1 with both the time-to relapse and continuous outcome models. We predict that rates of relapse and symptom burden among women randomized to MMB who discontinue AD will be significantly superior to those randomized to UC who discontinue AD.

H2b: Treatment Selection Algorithm: We predict that the use of a treatment selection algorithm will differentiate two profiles of women based on pre-treatment characteristics (those who are optimally suited to discontinue AD and engage MMB to minimize their risk of relapse, and those who should continue AD to minimize risk of relapse) and that women who are randomized to the algorithm indicated approach will have significantly lower risk of relapse and symptom burden than women who are randomized to their algorithm contraindicated approach.

Analysis for Specific Aim #3: To test the extent to which digital MMB engages putative targets.

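### The significance screen for covariates will almost never admit two of the three stratification factors to the Aim 1 relapse models; the loss is small and conservative, and a wording change removes it

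*Combined protocol and SAP*

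**What the plan says.** Section VI (Preliminary Analyses) compares the arms at baseline with a "Chi-square test for binary variables, Cochran Mantel Haenszel tests for categorical variables, and t-tests for continuous variables", at p < .05. The results then decide the covariates: "Variables that show significant group differences and predict outcome will be entered in analyses as covariates; AD exposure will be included as a covariate". AD exposure is the only covariate named.

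Section IV (UPWARD Study) allocates 300 women to each arm in blocks of four. Randomisation is "stratified based on number of prior episodes, antidepressant medication status (on medication or having discontinued at time of randomization), and baseline depressive severity", the last measured by PHQ-9 score. No cut points are given.

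The Aim 1 analysis text names a Cox model and a Fine-Gray model for relapse, and hierarchical linear models (HLM) for the PHQ-9. It lists no covariates or strata for the relapse models. H2a inherits this: "Our analysis will be the same as H1 with both the time-to relapse and continuous outcome models".

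AD use during follow-up is also recorded. Under Usual Care Characterization, "accurate tracking of care received, including pharmacotherapy, psychotherapy, and other interventions, will be conducted using the Treatment Tracking Sheet", and "This sheet will be completed by study staff for each subject throughout their participation". The Usual Care text says that the study will not constrain or influence women's "decisions about maintenance or discontinuation of AD for all participants".

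**The concern.** Stratified blocks exist to make the arms alike on the stratification factors. A screen that admits a variable only when the arms differ significantly on it will therefore pass over those factors because the randomisation worked. AD status escapes if that is what AD exposure means; prior episodes and baseline PHQ-9 do not. Baseline PHQ-9 can still enter the PHQ-9 HLM as the first outcome measurement, but the relapse models have no comparable stated route.

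When a prognostic factor is balanced by design and then left out of the analysis, the standard error does not take credit for the balance. The test becomes conservative and the hazard ratio (HR) is drawn towards 1. At stake is some power for relapse if the true effect is smaller than planned. Because the screen also looks at association with outcome, the covariate set stays open until outcomes have been seen.

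**Working it through.** **The plan's own figure.** The plan states 95.5% power for a 20-point difference with N = 600 and 30% attrition. That leaves 600 × 0.7 = 420, or 210 per arm. No control rate is stated; I assume 49% (the 19% relapse with MBCT in the Aim 2 power text, plus the 30% reduction in the Aim 1 power text read as points) against 29%. Power = Φ[(Δ − 1.96√(2p̄q̄/n)) / √((p₁q₁ + p₂q₂)/n)] = Φ[(0.20 − 1.96 × 0.0476)/0.0466] = Φ(2.29) = 98.9%. Control rates of 40 to 70% give 98.6 to 99.5%. With the 175 per arm of the continuous-outcome power text, the result is 97.2%, or 96.4% with continuity correction. So 95.5% does not reproduce from 210 per arm. Nothing below depends on it.

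**Step 1: can a stratification category pass the screen?** Assume two levels per factor, hence 8 strata. An unfinished block of four leaves at most 2 more women in one arm. Each level of a factor spans 4 strata, so its count differs between arms by at most 4 × 2 = 8, for example 154 against 146 of 300 per arm, or 0.027. Significance at a 50% prevalence needs 1.96 × √(2 × 0.5 × 0.5/300) = 0.080, or 24 women. The screen cannot fire. Simulation agrees: 0 of 5,000 trials for each factor.

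**Step 2: raw scores.** Variation within strata remains, so a t-test on raw scores can fire. Inputs: N = 600; PHQ-9 from 0 to 9 (the entry limit), cut at 5, with uniform, skewed or bell-shaped scores; prior episodes from 2 upwards, geometric with mean 3.5 or 5.0, cut at 3 or 4. Over 120,000 trials, p < .05 occurred in 0.00 to 0.09% for PHQ-9 and 0.13 to 2.48% for prior episodes. Separate runs with other cut points, some at N = 500, gave 0 to 0.04% and 0 to 1.3%; an unstratified variable passed about 5% of the time. The second condition, predicting outcome, can only lower these figures.

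**Step 3: power at a smaller effect.** Inputs, all assumed: three independent 50/50 factors, exponential relapse with 49% in usual care, 30% dropout, treatment HR 0.7, Cox Wald test at two-sided .05. The last four rows use 8,000 trials each (Monte Carlo standard error about 0.5 points); the first row is from a separate run.

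| HR: AD status | HR: each omitted factor | Power, AD status only | Power, all three | Loss, N = 600 | Loss, N = 500 |
|---|---|---|---|---|---|
| 2.0 | 1.2 | 74.6% | 74.8% | 0.2 | not run |
| 1.5 | 1.5 | 73.6% | 75.3% | 1.7 | 1.4 |
| 2.5 | 1.5 | 74.0% | 75.6% | 1.6 | 1.8 |
| 2.0 | 2.0 | 71.5% | 75.9% | 4.4 | 4.4 |
| 2.5 | 2.0 | 71.5% | 76.0% | 4.5 | 5.2 |

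N = 500 leaves out the Extension women, since "these final 100 participants will not receive any follow-up clinical interviews or relapse determination calls after the initial screening and baseline calls". A repeat of the first row gave 75.4% both ways. Repeats with all HRs at 1.5 gave 73.7 vs 75.2% and 74.3 vs 75.7%; with all at 2.0, 71.3 vs 75.4% and 72.2 vs 76.8%.

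**Step 4: type I error.** With AD status only it was 3.7 to 5.4% (3.5 to 4.1% with every factor HR at 2.5). With all three factors it was 4.4 to 5.6% (Monte Carlo standard error 0.24 points).

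**Step 5: the planned effect.** 49% against 29% corresponds to HR = ln(0.71)/ln(0.51) = 0.51. Power was above 99% with or without the omitted factors, at N = 600 and at N = 500.

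**The case against.** The strongest reply is that nothing happens at the effect the trial was sized for. That stands. An HR of 0.7 means about 49% against 1 − 0.51^0.7 = 38%, an 11-point difference, where the plan assumes 20. The documents give no prognostic HR for prior episodes or PHQ-9, and entry caps PHQ-9 at 9, so its effect may be weak. At 1.2 the loss is essentially nil, which is why the range starts at 0. It is also true that the plan does not forbid other covariates; it names none.

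Several stronger readings are tempting and are not supported.

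- *That the screen invalidates Aim 1 or produces false positives.* The simulated test is at or below its nominal level apart from simulation noise.
- *That 5 to 9 points of power are lost.* That needs every factor to have an HR of 2.5, a 2.5³ = 15.6-fold spread in hazard.
- *That usual-care relapse is 27% (19%/0.7).* This reads the 30% as relative. Reading the adjacent 20% the same way gives 27% against about 22%, with power near 25% at 210 per arm, irreconcilable with the stated 95.5%. I do not rely on it for the size of the loss.
- *That AD exposure means AD use after randomisation, so Aim 1 is not intent-to-treat.* The sentence gives no date and later use is recorded, but AD status at randomisation is already a stratification factor, and no text puts later use into the Aim 1 model.
- *That H2b claims a randomised AD comparison.* Its analysis text describes women as randomised to the indicated approach. Hypothesis 2b in Section II says that they receive it, the Usual Care text leaves AD use free, and the Aim 2 power text calls it a choice. This is a wording slip in an exploratory aim.

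**Conclusion.** The point holds for the stratification factors. As written, the screen will almost never bring prior episodes or baseline PHQ-9 into the Aim 1 Cox and Fine-Gray models. If they predict relapse, the test is slightly conservative: about 0 to 5 points of power at a treatment HR of 0.7 with omitted-factor HRs of 1.2 to 2.0. There is no type I error inflation, and the loss at the planned effect is negligible. The sizes rest on assumed cut points, prognostic HRs, usual-care relapse and treatment HR, and were simulated for the Cox model only. The conclusion on selection held under every cut point tried. This is a cheap improvement to the plan and no threat to its validity.

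**What to change.** For the Aim 1 relapse models (Cox and Fine-Gray) and the PHQ-9 HLM, replace the significance-test rule with:

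> Models adjust for the randomisation stratification factors: number of prior episodes, AD status at randomisation and baseline PHQ-9, coded as fixed before outcomes by arm are seen. In the PHQ-9 HLM, baseline PHQ-9 may enter as the baseline outcome. In Aim 1, AD exposure means AD status at randomisation; Aim 1 analyses that adjust for later AD use are secondary.

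Scope:

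- **H2a** takes the same adjustment for prior episodes and baseline PHQ-9. Its population remains defined by AD discontinuation, which can occur after randomisation, so the clause on secondary analyses does not apply to it.
- **Aim 3** HLMs may use the same factors.
- **Arm 2**, the 40-woman pilot, is outside this change.
- **H2b analysis text:** where women are described as randomised to an indicated or contraindicated approach, write 'receive', as in Section II.

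Cost: wording only. The three factors must be known in order to randomise, so no data are added. Their coding has to be fixed in advance. The reported HR becomes conditional on them and moves slightly: with a true HR of 0.68 and AD HR 2.0, the estimate went from 0.687 to 0.680 (omitted-factor HRs 1.5) and from 0.694 to 0.675 (HRs 2.0).
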